#### **9.5.5 Immunogenicity**

Immunogenicity data will be listed and frequency tables will be presented.

#### **9.5.6 Vital signs**

Vital signs data will be summarized by treatment together with changes from baseline, where baseline is defined as Day 1 predose. Figures of mean vital signs and mean changes from baseline profiles will be presented by treatment. Furthermore, values for individual subjects will be listed.

#### **9.5.7 Electrocardiogram (ECG)**

ECGs will be performed for safety monitoring purposes only and will not be presented.

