Subjects will be admitted to the clinical research unit (CRU) on Day -1. All doses will be administered in the morning of Day 1 as two 1-mL subcutaneous injections of 120 mg/mL solution of LY2951742. Subjects will be stratified to receive injections in the upper arm, abdomen, or thigh. Subjects will remain resident at the CRU until the procedures scheduled at 24 hours postdose have been completed on Day 2, or longer at the discretion of the investigator. All subsequent procedures will be performed on an outpatient basis.

Blood samples will be collected up to 20 weeks postdose to determine serum concentrations of LY2951742 for PK assessments and plasma concentrations of CGRP for PD assessments. Safety and tolerability will be assessed by recording of TEAEs, injection-site reactions (ISR), vital signs, 12-lead electrocardiograms (ECGs), physical examination, clinical chemistry, hematology, immunogenicity, and urinalysis.

Treatment Groups and Duration:

Subjects will be randomized in a 1:1 ratio to 240 mg LY2951742 as a manual PFS (reference) or 240 mg LY2951742 as an autoinjector (test). Each subject will receive a single dose of LY2951742 on a single occasion and have study procedures performed up to 20 weeks after study drug administration. Procedures scheduled for later than Day 2, 24 hours postdose will be performed on an outpatient basis, at the discretion of the investigator.

Number of Subjects:

Up to 160 subjects may be enrolled.

Statistical Analysis:

The $AUC(0-\infty)$; area under the concentration versus time curve from zero to time t , where t is the last time point with a measurable concentration ($AUC[0-t_{last}]$); and C_{max} will be log transformed and analyzed using an analysis of variance (ANOVA) model. The model will include fixed effects for injection device (PFS [reference] or autoinjector [test]), investigative site, and injection site. The least squares means for the PFS and autoinjector and the 90% confidence interval (CI) for the difference in means will be estimated from the ANOVA model and back transformed from the log scale to provide estimates of the geometric means and 90% CIs for the ratio of the geometric means.

Adverse events, product complaints, clinical laboratory parameters, vital signs, and ECG parameters will be assessed. They will be listed, and summarized using standard descriptive statistics.

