9.4.3. Electrocardiograms

For each subject, a single 12-lead digital ECG should be collected according to the Schedule of Activities (Section 2) and the study-specific recommendations included in the Manual of Operations for the study.

Any clinically significant findings from ECGs that result in a diagnosis and that occur after the subject receives the dose of the investigational product, should be reported to Lilly, or its designee, as an AE via the eCRF.

Electrocardiograms must be recorded before collecting any blood for safety or PK tests. Subjects must be supine for approximately 5 to 10 minutes before ECG collection and remain supine but awake during ECG collection. Electrocardiograms may be obtained at additional times, when deemed clinically necessary. All ECGs recorded should be stored at the investigational site.

Electrocardiograms will be interpreted by a qualified investigator (or designee) at the site as soon after the time of ECG collection as possible, and ideally while the subject is still present, to determine whether the subject meets entry criteria at the relevant visit(s) and for immediate subject management, should any clinically relevant findings be identified.

If a clinically significant finding is identified after enrollment, the investigator will determine if the subject can continue in the study. The investigator, or qualified designee, is responsible for determining if any change in subject management is needed, and must document his/her review of the ECG printed at the time of collection. Any new clinically relevant finding should be reported as an AE.

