10.3.1.2. Statistical Evaluation of Safety

Safety parameters that will be assessed include clinical laboratory parameters, vital signs, and ECG parameters. The parameters will be listed, and summarized using standard descriptive statistics. Additional analysis will be performed if warranted upon review of the data.

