### 3. INTRODUCTION

This SAP has been developed after review of the Clinical Study Protocol (final version dated 31 May 2016).

This SAP describes the planned analysis of the safety, tolerability, pharmacokinetic (PK) and pharmacodynamic (PD) data from this study. A detailed description of the planned TFLs to be presented in the clinical study report (CSR) is provided in the accompanying TFL shell document.

The intent of this document is to provide guidance for the statistical and PK analyses of data. In general, the analyses are based on information from the protocol, unless they have been modified by agreement between Eli Lilly and Company and Covance Early Clinical (EC) Biometrics. A limited amount of information concerning this study (e.g., objectives, study design) is given to help the reader's interpretation. This SAP must be signed off prior to first subject administration for this study. When the SAP and TFL shells are agreed upon and finalized, they will serve as the template for this study's CSR.

This SAP supersedes the statistical considerations identified in the protocol; where considerations are substantially different, they will be so identified. If additional analyses are required to supplement the planned analyses described in this SAP, they may be performed and will be identified in the CSR. Any substantial deviations from this SAP will be agreed upon between Eli Lilly and Company and Covance EC Biometrics and identified in the CSR. Any minor deviations from the TFLs may not be documented in the CSR.

This SAP is written with consideration of the recommendations outlined in the International Council on Harmonisation (ICH) E9 Guideline entitled Guidance for Industry: Statistical Principles for Clinical Trials and the ICH E3 Guideline entitled Guidance for Industry: Structure and Content of Clinical Study Reports.

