### **11. CHANGES FROM THE PROTOCOL SPECIFIED STATISTICAL ANALYSES**

There were no changes from the protocol specified statistical analyses.

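### SAP 9.5.7 drops the ECG summary, and on the natural reading the listing, that protocol 10.3.1.2 specifies, while SAP 11 declares no change

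*SAP*

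**What the plan says.** Protocol 10.3.1.2 (Statistical Evaluation of Safety) states: "Safety parameters that will be assessed include clinical laboratory parameters, vital signs, and ECG parameters". It continues: "The parameters will be listed, and summarized using standard descriptive statistics". The statistical paragraph of the protocol synopsis also names ECG parameters and says of the items it names: "They will be listed, and summarized using standard descriptive statistics".

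SAP 9.5.7 reads: "ECGs will be performed for safety monitoring purposes only and will not be presented".

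Three other parts of the SAP bear on this:

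- SAP 3 gives the SAP precedence over the protocol's statistical section, but adds that "where considerations are substantially different, they will be so identified".
- SAP 9.1 promises listings of all data held in the database.
- SAP 11 says: "There were no changes from the protocol specified statistical analyses".

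On the handling of the recordings, protocol 9.4.3 says "All ECGs recorded should be stored at the investigational site" and "Any new clinically relevant finding should be reported as an AE".

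**The concern.** A report built from this SAP would have no ECG summary and, on the natural reading of 9.5.7, no ECG listing. SAP 11 would meanwhile tell its reader that the protocol's analyses were carried over unchanged. What would be missing is the ECG parameter values by device arm, including any shift that an investigator did not judge clinically relevant. ECGs are among the methods the protocol names for assessing safety and tolerability, which is a secondary objective, so a reader of the protocol would expect to find them.

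**Working it through.** No arithmetic applies and the plan gives no figure to reproduce. The check is to set the protocol's commitment beside the SAP's provision for each safety-parameter group in protocol 10.3.1.2, and then to ask whether another SAP clause closes the gap.

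| Group in protocol 10.3.1.2 | Protocol asks for | SAP provides |
|---|---|---|
| Clinical laboratory | Listing and summary | SAP 9.5.4: chemistry and hematology listed and summarized; urinalysis listed only |
| Vital signs | Listing and summary | SAP 9.5.6: listed and summarized by treatment |
| ECG | Listing and summary | SAP 9.5.7: no presentation |

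ECG is the only one of the three groups with no output in its own SAP section.

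**Step 1, the summary.** No SAP section other than 9.5.7 deals with ECG output. SAP 9.1 limits summary statistics to data for which the SAP details them, and 9.5.7 details none. The summary is therefore lost on any reading.

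**Step 2, the listing.** Two general clauses might rescue it.

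- SAP 9.5.8 lists the remaining safety assessments, but only those its section has not already dealt with. ECG has its own subsection, so 9.5.8 does not reach it.
- SAP 9.1 lists databased data. The documents do not say whether ECG values are databased; protocol 9.4.3 says only that recordings are kept at the site. If the values are databased, 9.1 calls for a listing and 9.5.7 forbids it, so the SAP conflicts with itself. The specific clause would ordinarily prevail, and the listing is then lost. If they are not databased, 9.1 gives no listing, and the protocol's output could not be produced without further data entry.

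**Step 3, the declaration.** SAP 3 settles which document governs. It does not make SAP 11 true. SAP 11 is not restricted to substantial changes; it says there were none.

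**Step 4, whether ECG is the only departure.** It is not. Protocol Appendix 2 includes urinalysis among the laboratory tests, and protocol 10.3.1.2 asks for laboratory parameters to be summarized as well as listed. SAP 9.5.4 only lists urinalysis. Declaring ECG alone would leave SAP 11 inaccurate.

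**The case against.** The best defence is that this is a documentation slip of little consequence. The SAP takes precedence, and it states the ECG decision openly in a section of its own. The duty in SAP 3 covers only substantial differences and does not name SAP 11 as the place to identify them. Whether dropping a descriptive safety output is substantial is a matter of judgement. ECG is neither a primary nor a secondary endpoint. New clinically relevant findings go to the adverse-event record under protocol 9.4.3, and SAP 9.5.1 summarizes treatment-emergent events by treatment.

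Most of this stands, and it is why the point is minor. It does not rescue SAP 11, whose wording is unqualified and can be disproved by comparing two short sections. Nor does adverse-event reporting replace the promised output: it passes through the investigator's judgement, in an open-label study, and carries no parameter values.

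A reader might go further and infer that the safety objective cannot be met, or that ECG findings are being withheld. The documents support neither. The named safety endpoint is treatment-emergent adverse events, which the SAP reports in full, and 9.5.7 states the omission plainly.

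**Conclusion.** The inconsistency is real and minor. Loss of the ECG summary is certain from the text. Loss of the listing is conditional: it rests on 9.5.7 prevailing over SAP 9.1, or on the ECG values not being databased. It would be too strong to say that the SAP as a whole plainly rules out a listing, because 9.1 points the other way if the values are databased.

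SAP 11 is inaccurate for at least two items, the ECG presentation and the urinalysis summary. The pharmacokinetic comparison of the devices and its error rates are unaffected.

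The conclusion assumes that the table, figure and listing shells, which are a separate document not available here, follow SAP 9.5.7 as written.

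**What to change.** Preferred: rewrite SAP 9.5.7 so that ECG parameters are listed and summarized descriptively by device arm at the scheduled times. This restores what the protocol commits to and also removes any conflict with SAP 9.1. The cost is a few descriptive outputs, plus data entry if the values are held only at the sites.

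Alternative: if the sponsor intends to drop the presentation, for example because the values are not databased, SAP 11 must declare that with its reason. This costs a sentence, but it corrects only the record; the output is still missing.

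In either case, replace the no-changes sentence in SAP 11 with a complete list of departures found by comparing the SAP with protocol section 10 line by line. That list should include urinalysis being listed but not summarized (SAP 9.5.4), unless a urinalysis summary is added.

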#### **9.5.8 Other assessments**

All other safety assessments not detailed in this section will be listed but not summarized or statistically analyzed.

#### **9.5.9 Safety and Tolerability Statistical Methodology**

No inferential statistical analyses are planned.

### **10. INTERIM ANALYSES**

No interim statistical analyses are planned.

### **11. CHANGES FROM THE PROTOCOL SPECIFIED STATISTICAL ANALYSES**

There were no changes from the protocol specified statistical analyses.

### **13. DATA PRESENTATION**

#### **13.1 Derived Parameters**

Individual derived parameters (e.g. PK parameters) and appropriate summary statistics will be reported to three significant figures. Observed concentration data, e.g.  $C_{\max}$ , should be reported as received. Observed time data, e.g.  $t_{\max}$ , should be reported as received. N and percentage values should be reported as whole numbers. Median values should be treated as an observed parameter and reported to the same number of decimal places as minimum and maximum values.

#### **13.2 Missing Data**

Missing data will not be displayed in listings.

